Appendix Table 10: Maternal and Family Focused Preregistered Hypotheses

Domains (in gray) and sub-domains	Measure/Item source	Psychometrics	Age preregistered Primary Outcome	Age preregistered Secondary Outcome	Measures (All measures between grey lines measured during the same wave will be subject to multiple testing adjustments)
Household Economic Hardship					
Index of economic stress	MTO; Kling, Liebman, Katz, 2007		1, 2, 3, 4, 6, 8		
Age 1-4: Additive index of dichotomous variables (higher score=more stress):
 
 1. worried about expenses? (0: occasionally or never; 1: frequently or more) 2. whether spent more than income? (0: no; 1: yes) 3. missed rent or mortgage (0 if homeless or not missed; 1 if missed rent or mortgage) 4. Set aside rainy day funds for 1 mo (0: Yes 1: No) 5. Ability to cover expenses for 1 mo with loss of income (0: Yes; 1: No) 6. in past 12 mos, missed payments for water, gas, oil, electricity? (0: no or not applicable; 1: yes) 7. in past 12 mos, gas, water, electricity ever shut off? (0: no; 1: yes) 8. Since child's birth, have you ever been evicted or forced to leave? (0: No; 1: Yes). *changes to "in the past 12 months" for surveys at ages 2 through 4 9. needed medical or dental care and did not get it? (0=no; 1=yes) *item 9 dropped at age 4 owing to survey time constraint. 
Age 6,8: Additive index of dichotomous variables (higher score=more stress); expect less stress for high-cash group. In the past 12 months:
 
 1. have you ever missed a rent or mortgage payment? (1: Yes; 0: No) 2. did you ever miss a payment for oil, gas, water, or electricity? (1: Yes; 0: No/Not applicable, do not pay or does not have these utilities) 3. was your gas, water, or electricity ever shut off for nonpayment? (1: Yes; 0: No) 4. have you ever been forced to leave or were evicted from your home? (1: Yes; 0: No) 5. were you ever hungry, but didn't eat because you couldn't afford enough food? (1: Yes; 0: No) 6. did you receive free food or meals? (1: Yes; 0: No)
Maternal Hardship	BFY PIs		6, 8		
One item: 1. In the last 12 months, have you experienced an emergency need for extra money that would amount to \$500 or more? (1: Yes; 0: No) 1a. [If yes] Were you able to manage it? (Would you say: 1. Easily with no worries; 2. With some stress; 3. With a lot of difficulty; 4. Not at all, couldn't manage it) Expect less hardship for high-cash group. □

Household Poverty rate	US Census Bureau		1, 2, 3, 4, 6, 8		Measured using the Census Bureau's poverty thresholds by size of family and number of children. Age 6/8: Expect lower poverty rate for high-cash group.
Index of food insecurity*	Economic Research Service, USDA, 2012		1, 2, 3, 4		
Additive index of 6 dichotomized items (higher score=more food insecurity):
 
 1. Food didn't last, no \$ for more (0: Never true, 1: sometimes or often true) 2. Can't afford balanced meals (0: Never true, 1: sometimes or often true) 3. Cut size or skip meals (0: No; 1: Yes) 4. If yes to (3), how often? (0: only one or two months; 1: almost every month or some months) 5. Eat less than should (0: No; 1: Yes) 6. Hungry* (0: No; 1: Yes)

Appendix Table 10: Maternal and Family Focused Preregistered Hypotheses

Domains (in gray) and sub-domains	Measure/Item source	Psychometrics	Age preregistered Primary Outcome	Age preregistered Secondary Outcome	Measures (All measures between grey lines measured during the same wave will be subject to multiple testing adjustments)
Social Services Receipt					
Number of Benefits received by mother	Study PIs			1, 2, 3	Additive index of dichotomized items (higher score=more benefits received): 1. Food stamps SNAP (0: not currently receiving; 1: currently receiving) 2. Free or reduced childcare* 3. Early Head Start or HS* 4. Women, Infants and Children (WIC) 5. State Unemployment 6. Cash assistance/TANF* 7. Medicaid coverage for self 8. Housing assistance 9. LIHEAP / heat/AC assistance* *Indicates benefits that were not asked about at age 3. Note: Age 4 benefit index was not pre-registered because of the availability of administrative records for some of the benefits
Mother's Labor Market and Education Participation					
Time to labor market reentry from birth	Current Population Survey			1	Continuous outcome: # of months until mom's reentry into labor market from birth of child derived from the following items: 1. did you ever work for pay since child's birth? 2. in what months did you work for pay?
Time to full-time labor market reentry from birth	Current Population Survey			1	Continuous outcome: # of months until mom's full-time reentry into labor market from birth of child derived from the following items: 1. did you ever work full time since child's birth? 2. in what months did you work full time?
Mother's education and training attainment	Current Population Survey			1, 2, 3	Dichotomous variable indicating that mother participated in education and/or job training activities since birth* *changes to "in the past 12 months" for surveys at ages 2 and 3.
Mother's education attainment	Current Population Survey			6,8	Dichotomous variable indicating that mother participated in education in the past 12 months plus any degrees received. Expect higher educational attainment in high-cash gift group.
Mother's training attainment	Current Population Survey			6, 8	Dichotomous variable indicating that mother participated in job training activities in the past 12 months. Expect more training in high-cash gift group.

Appendix Table 10: Maternal and Family Focused Preregistered Hypotheses

Domains (in gray) and sub-domains	Measure/Item source	Psychometrics	Age preregistered Primary Outcome	Age preregistered Secondary Outcome	Measures (All measures between grey lines measured during the same wave will be subject to multiple testing adjustments)
Mother's Labor Market Participation	Current Population Survey			4, 6, 8	Dichotomous variable indicating whether mother is participating in the labor market using the item "do you currently work for pay?" We don't register group differences on employment and earnings impacts because of two offsetting arguments: i) income effects from our payments (our clawback arrangements with states preclude substitution effects) could lead mothers to opt for fewer work hours and possibly dropping out of the labor force altogether; or ii) our payment may enable the mothers in our study to engage in training activities and/or afford center-based child care that eventually boost earning and employment.
Maternal Earnings	PSID			4, 6, 8	Mother's Earnings in the previous calendar year. We don't register group differences on employment and earnings impacts because of two offsetting arguments: i) income effects from our payments (our clawback arrangements with states preclude substitution effects) could lead mothers to opt for fewer work hours and possibly dropping out of the labor force altogether; or ii) our payment may enable the mothers in our study to engage in training activities and/or afford center-based child care that eventually boost earnings
Child-Focused Expenditures					
Index of child-focused expenditures (since birth)	Lugo-Gil, Yoshikawa, 2006			1	Additive index of the following dichotomous items (higher score=more purchased): Since child's birth, purchased... 1. Crib? 2. Car seat? 3. High chair? 4. Safety covers for outlets? 5. Latches for cabinets? 6. Gate? 7. Smoke detector? 8. books (yes/no)?
Index of child-focused expenditures	Lugo-Gil, Yoshikawa, 2006, and Schild et al., 2003			1, 2, 3, 4, 6, 8	Continuous dollar amount of age-relevant items. Past 30 days, total \$ amount spent on... Age 1: 1. books 2. toys 3. clothes 4. diapers 5. videos; Age 2-4: 1. books 2. toys 3. clothes 4. activities 5. videos. Age 6/8: 1. clothing 2. electronic devices 3. toys 4. school materials 5. activities. 6. medical expenses 7. child care 8. travel Expect higher spending for high-cash group.
Index of expenditures on all children in the household, including target child	Schild et al., 2003			6, 8	Past 30 days, total \$ amount spent on all children in household. Expect higher spending for high-cash group. 1. clothes 2. electronic devices 3. toys 4. school materials 5. activities 6. medical expenses 7. child care 8.travel
Cost of paid child care	National Study of Early Care and Education			1, 2, 3, 4	Out of pocket spending on child care last month. 1. altogether, about how much money did you spend out-of-pocket on all of [CHILDNAME]'s child care arrangements last month? Note: Age 4: dropped wording "out-of-pocket"
Use of center-based care	National Study of Early Care			1	1. Has child spent any time in childcare or day care? (Y/N)

**Appendix Table 10: Maternal and
Family Focused Preregistered Hypotheses**

Domains (in gray) and sub-domains	Measure/Item source	Psychometrics	Age preregistered Primary Outcome	Age preregistered Secondary Outcome	Measures (All measures between grey lines measured during the same wave will be subject to multiple testing adjustments)
Use of center-based care	of Early Care and Education			2, 3, 4	1. Has child spent 5 or more hours in a child care or day care center last week? (Y/N)
Housing and Neighborhoods					
Index of perceptions of neighborhood safety	MTO; Kling, Liebman, Katz, 2007			1, 2, 3	Additive index of two items (higher score=feels more safe). 1. how safe during day? (3: very safe, 2: safe, 1: unsafe, 0: very unsafe) 2. how safe during night? (3: very safe, 2: safe, 1: unsafe, 0: very unsafe)
Index of housing quality	MTO; Kling, Liebman, Katz, 2007			1	Additive index of 7 items (higher score=higher quality): 1. Bad walls (0: big problem; 1: small problem; 2: not problem) 2. bad plumbing 3. rodents 4. cockroaches 5. bad windows 6. bad heat 7. overall condition (3: excellent, 2: good 1: fair, 0: poor)
				2	Additive index of 9 items (higher score=higher quality): 1. Bad walls (0: big problem; 1: small problem; 2: not problem) 2. bad plumbing 3. rodents 4. cockroaches 5. bad windows 6. bad heat 7. bad air condition 8. bad locks 9. overall condition (3: excellent, 2: good 1: fair, 0: poor)
Homelessness	MTO; Kling, Liebman, Katz, 2007			1, 2, 3	Dichotomous indicator of whether the mother has ever been homeless or in a group shelter (age 1 "since birth", age 2-3 "in the past 12 months"): 0: No 1: Yes
Excessive Residential mobility	MTO; Kling, Liebman, Katz, 2007			1, 2, 3	Moved three or more times since birth of baby* (Y/N) *changes to "in the last 12 months" for surveys at ages 2 and 3
Neighborhood poverty	Kling, Liebman, Katz, 2007			1, 2, 3, 4, 6, 8	# of residents below poverty line in census tract divided by total number of residents in census tract. Age 6/8: Expect less neighborhood poverty in the high-cash group.

Appendix Table 10: Maternal and Family Focused Preregistered Hypotheses

Domains (in gray) and sub-domains	Measure/Item source	Psychometrics	Age preregistered Primary Outcome	Age preregistered Secondary Outcome	Measures (All measures between grey lines measured during the same wave will be subject to multiple testing adjustments)
Family and Maternal Perceived Stress					
Perceived stress	Cohen et al., 1994, 1983	alpha: .86		1, 2	Perceived Stress Scale (PSS): additive index of 9 items (0: never; 1: almost never; 2: sometimes; 3: fairly often; 4: very often) 1. upset because of something unexpected 2. felt unable to control important life things 3. felt nervous and stressed 4. confident in ability to handle personal probs (reverse coded - rc) 5. couldn't cope with all things to do 6. control of irritations in life (rc) 7. "on top of things" (rc) 8. angered bc of things outside control 9. could not overcome difficulties
				3	Perceived Stress Scale (PSS): additive index of 10 items (0: never; 1: almost never; 2: sometimes; 3: fairly often; 4: very often) 1. upset because of something unexpected 2. felt unable to control important life things 3. felt nervous and stressed 4. confident in ability to handle personal probs (reverse coded - rc) 5. couldn't cope with all things to do 6. control of irritations in life (rc) 7. "on top of things" (rc) 8. angered bc of things outside control 9. could not overcome difficulties 10. felt things were going "your way" (rc)~
Parenting stress	Items 1-4: Project GAIN Items 5-7: PSID- Child Development Supplement			1, 2 (originally also registered for age 4 and then dropped)	Aggravation in Parenting Scale: additive index of 7 items (0: Strongly agree-5: Strongly disagree): 1. confidence in parenting abilities 2. feels good about parenting abilities 3. thinks good parent 4. kids will say she was wonderful 5. giving up more for kids than ever expected 6. feels trapped (rc) 7. unable to do different things bc of kids (rc) Note: Index dropped from age 4 survey owing to time constraints

Appendix Table 10: Maternal and Family Focused Preregistered Hypotheses

Domains (in gray) and sub-domains	Measure/Item source	Psychometrics	Age preregistered Primary Outcome	Age preregistered Secondary Outcome	Measures (All measures between grey lines measured during the same wave will be subject to multiple testing adjustments)
Maternal Happiness and Optimism					
Global happiness	The General Social Survey from NORC			1, 2, 3, 6, 8	One-item with 3-point response scale. Age 1-3: "Taken altogether, how happy are you these days?" (0: not happy; 1: pretty happy; 2: very happy) One-item with 3-point response scale. Expect higher score for high-cash group. Age 6/8: "Taken all together, how would you say things are these days, would you say that you are 1. very happy 2. pretty happy or 3. not too happy?" Expect higher score for high-cash group.
Maternal Agency	Snyder et al., 1991	alpha: .86 test-retest: .81		1, 2, 3	The Adult Hope Scale: additive index of 8 items with 5-point response scale (0: definitely false; 5: definitely true) 1. think of ways to get out of a jam 2. energetic pursuit of goals 3. lot of ways around any problem 4. ways to get what's important 5. solves problems 6. past has prepared me for future 7. pretty successful in life 8. meets goals set for oneself
Maternal Physiological Stress					
Maternal hair cortisol	Ursache et al., 2017			1, 4	At age 1, we attempted to collect maternal hair cortisol for all in-person visits, prior to the onset of the pandemic (when data collection became limited to phone-based survey administration only). This resulted in a hair sample being collected from 409 of the 605 mothers who participated in an in-person visit, with large racial and ethnic differences in willingness to provide a sample. At age-4, we attempted to improve collection rates following focus groups and the development of informational videos. However, the first several months of data collection again revealed large racial and ethnic differences in willingness to provide a hair sample, due to both cultural and practical reasons. Because of the large amounts of non-random missing data, which would both compromise our statistical power and limit the generalizability of any findings, we dropped hair cortisol from the age-4 data collection procedures on October 25, 2022.
Maternal Executive Function					
Executive Function	Carlson, 2017; Carlson & Zelazo 2014; Reflection Sciences 2021	ICC=0.69		4, 6, 8	Minnesota Executive Function Scale (MEFS). Age 6,8: We expect a higher value of the maternal MEFS standardized score for the high-cash gift group mothers than the low-cash gift mothers. Higher scores indicate better performance.

Appendix Table 10: Maternal and Family Focused Preregistered Hypotheses

Domains (in gray) and sub-domains	Measure/Item source	Psychometrics	Age preregistered Primary Outcome	Age preregistered Secondary Outcome	Measures (All measures between grey lines measured during the same wave will be subject to multiple testing adjustments)
Maternal Attentional Resources					
Scarcity-Primed Inhibitory Control and Attention	Gershon et al., 2013; Slotkin et al., 2012; Zelazo et al., 2013	Test-retest: English 3-15 years: ICC=0.95; 20-85 years: ICC=0.83. Spanish 18-85 years: $\rho=.65$	6, 8		NIH Toolbox Flanker Inhibitory Control and Attention Test. Age-corrected standardized score. We expect a higher value of the maternal Flanker score for the high-cash gift group mothers than the low-cash gift mothers. Higher scores indicate better performance. Prior to the Flanker administration, respondent/mother will be asked to listen and reflect for a minute on these questions: "Imagine that an unforeseen event requires of you an immediate \$1,000 expense. Are there ways in which you may be able to come up with that amount of money on a very short notice? How would you go about it? How stressful would it be to manage this?"
Maternal Mental Health					
Index of maternal depression	Kroenke & Spitzer, 2002			1, 2, 3, 4, 6, 8	PHQ-8: additive index of 8 items (0: not at all; 1: several days; 2: more than half of days; 3: every day) Age 6/8: We expect less depression in the high- as opposed to low-cash group. 1. little interest or pleasure doing things 2. feeling down, depressed, hopeless 3. trouble sleeping or sleep too much 4. feel tired and no energy 5. poor appetite or overeating 6. feel like a failure 7. trouble concentrating 8. moving slowly or fidgety
Index of maternal anxiety	Steer & Beck, 1997 Spitzer et al., 2006	alpha: .92 test-retest: .75 alpha: .92 test-retest: .83		1, 3 2, 3, 4, 6, 8	Beck Anxiety Inventory: additive index of 21 common anxiety symptom items (0: not at all; 1: mildly; 2: moderately; 3: severely bothersome) GAD-7: additive index of 7 items (0: not at all; 1:several days; 2: more than half the days; 3: nearly every day) Age 6/8: We expect less anxiety in the high- as opposed to low-cash group. 1. nervous and anxious 2. no control worrying 3. worrying too much 4. no relaxing 5. restless 6. annoyed and irritable 7. afraid
Maternal Substance abuse^x					
Alcohol and cigarette use	MTO; Kling, Liebman, Katz, 2007			1, 3	Additive index of the following items (0: never in last year; 1: less than 1x per month; 2: several times per month; 3: several times per week; 4: everyday): 1. How often do you smoke cigarettes? 2. How often drink alcohol?

Appendix Table 10: Maternal and Family Focused Preregistered Hypotheses

Domains (in gray) and sub-domains	Measure/Item source	Psychometrics	Age preregistered Primary Outcome	Age preregistered Secondary Outcome	Measures (All measures between grey lines measured during the same wave will be subject to multiple testing adjustments)
Opioid use	MTO; Kling, Liebman, Katz, 2007			1, 3	Number of times of opioid use in the past year (0: never in last year; 1: less than 1x per month; 2: several times per month; 3: several times per week; 4: everyday):
Chaos in Home					
Index of chaos in the home	Evans et al., 2005	alpha: .77 test-retest: .93		1, 2	Home Environment Chaos Scale: additive index of 20 items (higher score=more chaos): (0: not true; 1: true) 1. can find things (reverse coded - rc) 2. little commotion in home (rc) 3. always rushed 4. can "stay on top of things" (rc) 5. always late 6. "zoo" in home 7. can talk w/o interruption (rc) 8. always a fuss 9. family plans don't work out 10. can't hear oneself think at home 11. drawn into others' arguments 12. can relax at home (rc) 13. phone takes up a lot of time 14. atmosphere is calm at home (rc) 15. regular morning routine (rc) 16. eat together during daily (rc) 17. evening routine with child (rc) 18. regular late afternoon routine with child (rc) 19. child goes to bed at regular time (rc) 20. set aside for talking with child daily (rc)
Maternal Relationships					
Physical Abuse	Fragile Families and Child Wellbeing Study			1,2	1. Ever abused? (1: yes; 0: no)
Frequency of Arguing				1,2	1. How often argue about things that are important to you? (1: never; 2: rarely; 3: sometimes; 4: often; 5: always)

Appendix Table 10: Maternal and Family Focused Preregistered Hypotheses

Domains (in gray) and sub-domains	Measure/Item source	Psychometrics	Age preregistered Primary Outcome	Age preregistered Secondary Outcome	Measures (All measures between grey lines measured during the same wave will be subject to multiple testing adjustments)
Relationship quality				1	Additive index of the following items (higher score=higher qual rel) 1. Partner fair and willing to compromise? (3: Often; 2: sometimes; 1: never) 2. partner expressed affection or love? (3: Often; 2: sometimes; 1: never) 3. partner insulted or criticized you or your ideas (0: Often; 1: sometimes; 2: never) 4. partner made you feel down or bad about yourself during an argument? (0: Often; 1: sometimes; 2: never) 5. partner encouraged or helped you to do things that were important to you? (2: Often; 1: sometimes; 0: never) 6. partner isolated you? (0: Often; 1: sometimes; 2: never) 7. partner hurt you physically (0: Often; 1: sometimes; 2: never) 8. partner sexually abused you? (0: Often; 1: sometimes; 2: never) 9. partner listened to you? (3: Often; 2: sometimes; 1: never) 10. partner made you feel afraid? (0: Often; 1: sometimes; 2: never) 11. partner threatened or hurt your child/children?+ (0: Often; 1: sometimes; 2: never)
				2, 3	Dichotomous indicator of current or recent relationship quality, where poor quality is defined as 1 if the mother is in a relationship and has a score of 26 or below on the relationship quality scale (approximately the bottom tercile of the low cash gift group distribution of scores) and a 0 either if the mother is not in a relationship or is in a relationship and has a relationship quality index score of 27 or above (approximately in the top two terciles of the distribution).
Maternal Physical Health					
Global health	Idler & Benyamini, 1997			1, 2, 6, 8	One item with 5-point response scale "overall, how would you describe your health..." (1:poor - 5:excellent) Age 6/8: Expect better health for high-cash group
Sleep	Yu et al., 2012			1, 3	Additive index of the following items (higher score=higher qual sleep): 1. Quality of sleep (0: very poor-5: very good) 2. Difficulty falling asleep (0: not at all; 5: very much) (rc) 3. Felt tired (0: not at all-5: very much) (rc)
Mother's BMI	CDC scales			4, 6, 8	Age 4: Measured by CDC BMI percentile scales Age 6, 8: Dichotomous measure based on CDC BMI percentile scales We expect to see a reduced percentage of overweight or obese (BMI greater than or equal to 25) mothers in the high-cash gift group compared to the low-cash gift group. We will report mean BMI of the two groups in descriptive analyses.
Parent-Child Interaction Quality					
Adult word count	Xu et al (2009), LENA foundation			1	Measured using LENA processing software

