We will apply our regression estimation strategy to the assessment-based measures of cognitive, language, self-regulation, and socio-emotional functioning and EEG measures of brain activity as outlined in Appendix Tables 7. Further information on the EEG hypotheses and analysis plan is described in the section titled *Age-4 Resting EEG Hypotheses and Analysis Plan* below. To investigate family process impacts, we will apply our estimation strategy to maternal and family measures gathered at child ages 1, 2, 3, and 4 as shown in Appendix Table 8.

Attrition. The greatest threat to internal validity is potential bias from sample attrition overall, within site, and differential attrition rates by treatment status overall and within site. We will carefully track response rates by site, by treatment status across sites, and then treatment status within site. Response rates have been very high at ages 1. Of the original 1,000 recruited participants, we secured interviews with 931 at age 1, 922 at age 2, and 922 again at age 3. We expect at least 800 completed cases in our age-4 lab visit.

We will also conduct sensitivity checks to evaluate whether missing data might be biasing estimates. Most sample attrition that is systematically related to our outcomes of interest (Y) would presumably also be related to the distribution of baseline characteristics (X), and so bias due to sample attrition would be evident if our estimates are sensitive to conditioning on baseline characteristics. Some attrition may be due to time-varying (or unobserved) characteristics, and we can approach this problem in two ways. First, we will examine the sensitivity of our results to worst-case bounds, which enable us to bracket the true effects of our treatment without imposing any assumptions about the unobserved outcomes of participants (Manski, 1989; Manski, 1990; Manski, 1995). A second approach to addressing the problem of missing data will be to use multiple imputation strategies with all available data, (including all survey and administrative data on outcomes and predictor variables). Multiple imputation is an appropriate method if, conditional on all observed information, data are missing at random. Finally, because we have permission to collect administrative data from over 75% of mothers, we will be able to compare survey respondents and survey non-respondents on formal earnings and receipt of income from social programs.

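### SAP Appendix Table 10: the only printed relationship-quality key has a maximum of 25, which is incompatible with the 26/27 cut that defines the outcome at ages 2 and 3

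*SAP*

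**What the plan says.** The entry is in SAP Appendix Table 10, domain Maternal Relationships, sub-domain Relationship quality. It has two rows, and both are secondary outcomes.

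**Age 1 row.** This is an additive index of 11 items, with higher totals meaning a better relationship. Each item carries its own scoring, and the scoring is not uniform. Items 1, 2 and 9 run from 1 to 3; for example "Partner fair and willing to compromise? (3: Often; 2: sometimes; 1: never") and "partner expressed affection or love? (3: Often; 2: sometimes; 1: never"). The unfavourable items run from 0 to 2; for example "partner insulted or criticized you or your ideas (0: Often; 1: sometimes; 2: never"). Item 5 is favourable, like items 1, 2 and 9, but is scored from zero: "partner encouraged or helped you to do things that were important to you? (2: Often; 1: sometimes; 0: never"). The notes under the table add that item 11 could not be used at age 1, so the index had one item fewer there.

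**Ages 2 and 3 row.** The outcome becomes a yes/no indicator. It takes the value 1 for any partnered mother who "has a score of 26 or below on the relationship quality scale (approximately the bottom tercile of the low cash gift group distribution"). It takes the value 0 for mothers without a partner, and also for any partnered mother who "has a relationship quality index score of 27 or above (approximately in the top two terciles of the distribution"). This row prints no item key. It refers only to the scale and index by name.

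**The concern.** A cut meant to divide partnered mothers about one third to two thirds has to lie inside the range of the score. On the key in the same table, both 26 and 27 lie above the highest possible total. Someone coding the variable from the table would put every partnered mother in the poor group and every unpartnered mother in the other. The result would be a measure of partnering labelled as relationship quality, and an effect of the cash gift on forming or leaving partnerships could be reported as an effect on quality.

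The outcome is secondary, but it carries some weight in its domain. At age 3 it is the only preregistered measure listed under Maternal Relationships, because physical abuse and frequency of arguing are listed for ages 1 and 2 only. At age 2 it shares a multiple-testing family with those two measures, so a wrongly built indicator would also enter their adjusted p-values.

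**Working it through.** **Inputs**, all from the Relationship quality rows of SAP Appendix Table 10:

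- Items 1, 2 and 9: minimum 1, maximum 3 (three items).
- Items 3, 4, 5, 6, 7, 8, 10 and 11: minimum 0, maximum 2 (eight items).
- Index: simple sum of the items.
- Cut: poor at 26 or below, not poor at 27 or above.
- Stated split: about the bottom tercile against about the top two terciles.

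**Range on the printed key**

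- Maximum = 3 × 3 + 8 × 2 = 9 + 16 = 25.
- Minimum = 3 × 1 + 8 × 0 = 3.

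Enumerating all 3^11 = 177,147 response patterns confirms that none totals 26 or more. The stated split therefore cannot be reproduced: on the printed key 100% of partnered mothers score 26 or below and 0% score 27 or above.

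**Does a small slip in the key explain it?** Four of the eleven items are favourable (1, 2, 5, 9) and seven unfavourable (3, 4, 6, 7, 8, 10, 11). The variants below other than the printed key are assumptions, apart from the loss of item 11, which the table notes report for age 1.

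| Scoring | Range | Can a mother reach 27? |
|---|---|---|
| Printed key, 11 items | 3 to 25 | No |
| Printed key without item 11 | 3 to 23 | No |
| Item 5 also scored 1–3 | 4 to 26 (4 × 3 + 7 × 2) | No |
| All items 0–2 | 0 to 22 | No |
| All items 1–3 | 11 to 33 | Yes |
| Favourable items 0–2, unfavourable items 1–3 | 7 to 29 (4 × 2 + 7 × 3) | Yes |

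Correcting the odd scoring of item 5 is not enough. At least two codings outside the document would make 26/27 usable.

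**Can the cut be translated to the printed key?** Only if the coding actually used is known.

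- If all items were scored 1–3, eight items sit one point higher than printed, and the equivalent cut is 26 − 8 = 18 (18/19).
- If favourable items were 0–2 and unfavourable items 1–3, items 1, 2 and 9 sit one point lower and seven items one point higher, a net shift of −3 + 7 = +4. The equivalent cut is 26 − 4 = 22 (22/23).

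The two answers differ by four points, and the documents give no ground for choosing between them.

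**The case against.** The strongest reply is that the mismatch is one of documentation and nothing was miscoded. A reader might infer from the arithmetic that every partnered mother was in fact classed as having a poor relationship. The documents do not support that. The sentence that sets the cut says it falls near the bottom tercile of the low-cash group, with about two thirds at 27 or above. Scores on a 3 to 25 scale could not produce that description, so it was most naturally written from data scored on a wider range. This part of the reply stands, and it limits the finding to an inconsistent definition.

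Three further points on that side:

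- **The key is printed only in the age 1 row.** Applying it at ages 2 and 3 is an inference from the shared name. It is a reasonable one: both rows carry one label, the later row gives no key, and the same table reprints items where an index changes with age (perceived stress, housing quality, parent-child activities). If the scoring did change, the change is undocumented here.
- **The governing plan may be elsewhere.** The SAP's opening says that analytic plans for ages 1 to 3 are on the registry's record history, and it calls the appendix tables summary charts. The missing key may be there. It would still need to agree with this table, which is presented as covering all hypotheses and measures at every age.
- **It is not shown that this row will be run as printed.** The Phase 1 estimation section says "we will apply our estimation strategy to maternal and family measures gathered at child ages 1, 2, 3, and 4", but that sentence goes on to cite Appendix Table 8, which is not among the documents reviewed. It cannot be used as evidence about this row of Table 10.

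It can also be said that anyone applying the printed key would notice at once that no mother scores 27 or above. That makes a silent error less likely, but it would not tell them the correct key.

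**Conclusion.** The printed key (3 to 25) and the 26/27 cut cannot both be right for the same score. This rests on the item scoring as printed, on simple addition, and on the age 1 key being the one to which the ages 2 and 3 row refers. Under those conditions the not-poor category is empty among partnered mothers, and the indicator equals being in a relationship.

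The arithmetic is certain. Which element is wrong is not: a misprinted or undocumented key is likelier than a wrong cut, given the tercile description. Actual misclassification is not shown. The reach is one preregistered secondary outcome at ages 2 and 3, together with its multiple-testing family at age 2. No primary outcome is affected. It is worth correcting because the outcome cannot be reproduced from the table as it stands.

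**What to change.** 1. Confirm from the analysis code which item scoring produced the age 2 and age 3 variable.
2. Print that key in Appendix Table 10 for ages 2 and 3, with the number of items and the possible range, beside a cut on the same scale. If the age 1 scoring differed, say so, and state whether the uneven scoring of item 5 is intended.
3. Re-derive the indicator, and the age 2 adjusted p-values in its family, only if the printed key was used.

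Do not substitute 18/19 on the printed key. It holds only if every item was scored 1–3, which the documents do not state, and another workable coding would give 22/23.

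The cost is a check of existing code and a table correction. No new data are needed, and nothing is re-analysed unless the check shows that the printed key was applied.
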